For the no-intervention comparison arm, patients will be identified from the list of approximately 1,800 remaining patients who were deemed eligible but not yet recruited before all 80 pilot intervention patients are accrued. From this list, we will select 80 patients with similar age and sex characteristics as trial participants. Patients in this no-intervention comparison group will not be contacted, will receive no intervention, and only their routinely collected clinical data will be used for the retrospective comparison evaluation (i.e. the same existing clinical data elements used to assess outcomes for the trial groups), so they will not receive contact or specific recruitment materials. Detailed information about consent and HIPAA waivers is described below in "CONSENT PROCESS" section

Research Activity #4: For the semi-structured interviews, the database manager will draw names randomly from the pragmatic trial recruitment list until 20 patients have completed the interview. After obtaining approval from the primary care provider, a research assistant (RA) will send a lead letter by email to patients and then contact each patient by phone between 8 and 12 weeks after being sent their initial MyChart message. Purposeful sampling will be used to ensure that the sample is representative of between 5 and 10 patients who did not complete the goal setting step and 10 to 15 patients who did complete that step. Phone interviews will be conducted for both patients who did not complete the goal setting step and patients who did complete the goal setting step. The RA will explain the research and assist interested participants to provide informed consent prior to completion of a one-time interview.

COMPENSATION FOR PARTICIPATION IN RESEARCH ACTIVITIES

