Because the proposed trial is a pilot and feasibility study, we have chosen a sample size needed to design the intervention to be implemented and sustained within routine practice workflows and to be usable to patients. Primary care practices in the Northwestern Medical Group (NMG) central region deliver care to more about 183,000 unique adult patients annually. Our pilot study will take place at the Galter Primary Care (GPC) site, which is relatively close to the medical campus and sees a patient case mix that mirrors the larger NMG patient population. About 70% of GPC patients have used MyChart in the past year, and 32% of those (N=5,967) meet the study's eligibility criteria. Thus, recruitment of the proposed sample will be feasible.

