## Analysis Plan

**Data Sources & Collection:** The primary outcome of interest was the percent of eligible patients who commit to a weight goal and reach 5% or greater weight loss at 6 months. Key secondary outcomes include the percent of eligible patients who set a weight goal (regardless of weight loss), and mean changes in pragmatically collected cardiometabolic risk factors. As a feasibility study, we also estimated costs per person per year for intervention delivery.

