We assessed the feasible capture of body weight measures from two pragmatic data sources: electronic health records and cellular-enabled, wireless body weight scales (eScales), which were provided to all participants at the time of randomization. We extracted the date and value of all body weight recordings in the electronic health record of each eligible patient participant during the 12 months before his/her study randomization date (each occurred between 12/16/2019 and 1/6/2020). We also extracted the date and value for all body weight measures available from either the electronic health record or from eScale transmissions during the 15-month period after each individual's study randomization. The last electronic health record weight measure prior to the randomization date served as the baseline body weight for constructing the primary weight change outcome variable. The electronic health record weight measure closest to the date of randomization plus 180 days (6 months) was selected for the follow up body weight measure for the primary outcome analysis. For patients who did not have a follow up weight value in the electronic health record between 6 months +/- 3 months, we searched the electronic health record for a weight value between 12 months +/- 3 months. For participants missing 6-month weight values, we imputed their 6-month value as equal to one half the distance between the baseline and 12 month value. For participants missing both a 6- and 12-month weight value in the electronic health record, we used the eScale weight value closest to 6 months +/- 3 months. Finally, if individuals were missing all of these weight values, we assumed conservatively for the primary outcome analysis that the participant failed to reach the 5% weight loss threshold. All blood pressure, A1c, and cholesterol test results were extracted similarly from the electronic health record. As this was a small pilot trial, when analyzing mean change at different time points, we analyzed only those patients with available outcome measures and did not use advanced imputation approaches for replacing missing values.

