**Statistical Analysis:** We examined univariate and bivariate descriptive statistics and conducted chi-square or Fisher exact tests to compare all patients randomized to intervention and control arms on the proportion that reached the dichotomous primary outcome of clinically meaningful weight loss at 6 months. We conducted t-tests to compare all patients with available outcome measures in each study arm with respect to all pre-specified, continuous outcomes (e.g., mean changes in body weight, systolic blood pressure, hemoglobin A1c, total cholesterol, and non-HDL cholesterol). Multivariate models (ANCOVA and multivariate logistic regression) were used to estimate adjusted means (continuous variables) or proportions (categorical variables) for each pre-specified outcome. We explored stratified analyses by age and by sex to understand if preliminary outcome differences appeared to vary with these biologic variables.

Input from health system leaders and study team members were used to identify the principal "ingredients" of study interventions. Inputs included personnel, supplies, contract services, and facility and administrative costs, all from the perspective of the health system. Administrative data on the number and type of contacts made between nurses and study participants, as well as interviews with staff to identify time spent in other activities was used to estimate %FTE spent with patients in each study arm over 6 and 12 months. Costs of eScales and community intervention program fees were estimated from the invoice amounts to estimate cost per person and overall. One-time development or startup costs for health IT was estimated from contract amounts and invoiced payments for work performed. Operational or maintenance costs for IT support was estimated from interviews of IT staff members, who were asked to estimate hours per week spent supporting the intervention components. Research-only costs were excluded from intervention cost estimations. Since many health payers currently reimburse for lifestyle interventions costing between \$400 and \$800 per person annually, preliminary estimates for intervention costs equal or less than this were considered supportive of health system sustainability and were used as a threshold for proceeding to a larger future trial that will include a more intensive net cost and cost-effectiveness analysis.

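### Does the cost threshold for going on to a larger trial fail because it names no single cut-off and no divisor for shared IT cost?

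*SAP*

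**What the plan says.** The cost text is in the SAP's Analysis Plan. Under Data Sources & Collection, the SAP describes the trial as a feasibility study and states the unit: "we also estimated costs per person per year for intervention delivery".

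The method is under Statistical Analysis, from the health system's perspective:

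- **Nurse time:** contact records and staff interviews give the share of full-time effort spent on patients in each arm, over 6 and 12 months.
- **Scales and program fees:** "Costs of eScales and community intervention program fees were estimated from the invoice amounts to estimate cost per person and overall".
- **One-time IT:** "One-time development or startup costs for health IT was estimated from contract amounts and invoiced payments for work performed".
- **Recurring IT:** "Operational or maintenance costs for IT support was estimated from interviews of IT staff members, who were asked to estimate hours per week" spent in support of the intervention.
- **Excluded:** research-only costs.

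The comparator is what many payers reimburse for lifestyle interventions, $400 to $800 per person annually. The SAP says that "intervention costs equal or less than this were considered supportive of health system sustainability and were used as a threshold for proceeding" to a larger trial, which is to include a fuller net cost and cost-effectiveness analysis.

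**The concern.** The threshold refers back to a range, so two cut-offs could be read from it. Recurring IT support is collected as weekly hours, which is a total for the system, and one-time IT cost is a contract or invoice total. The SAP gives neither a divisor. It also does not say whether one-time cost enters the compared figure, or over how many years.

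A fixed total gives a higher per-person cost over a small pilot than over a large population. If the IT total were large, the decision to proceed could turn on the divisor and not on what the intervention costs to deliver. That matters because the SAP ties the comparison to that decision.

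**Working it through.** There is no cost result in the documents to reproduce. The check is how far the unstated choices could move the comparison.

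**Cut-off.** If payers reimburse programs costing up to $800, a cost at or below what they reimburse is a cost of at most $800. I use that reading.

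**Divisors.**

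- 40 and 80: the Protocol (Study Activities, Phase 2) assigns 80 patients, 40 per arm. Both arms get approaches 1 to 4 (Research Activity #3), and the SAP says of the scales "which were provided to all participants at the time of randomization". IT support therefore served up to 80 patients. The part that serves only approach 5 served 40.
- About 1,800: Recruitment Methods describes "approximately 1,800 remaining patients who were deemed eligible but not yet recruited". This is the pool from which untreated comparison patients are drawn.
- 5,967: the closing resources section says "About 70% of GPC patients have used MyChart in the past year, and 32% of those (N=5,967) meet" the eligibility criteria. This supports the claim that recruitment is feasible.

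The last two counts describe different groups, and neither is offered for costing. Most of these people received nothing from the intervention, so they do not fit a cost per person for delivery. The pilot counts remain, and they differ by 80/40 = 2.

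**Formula.** Cost per person = V + F/N, where V is other running cost per person, F is yearly IT support and N is the divisor. The result differs between 40 and 80 only when 800 − F/40 < V ≤ 800 − F/80.

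**Illustration at an assumed $75 an hour.** F = hours per week × 52 × $75.

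| Hours/week | F | F/40 | F/80 | V for which the result differs |
|---|---|---|---|---|
| 2 | $7,800 | $195.00 | $97.50 | above $605.00, up to $702.50 |
| 5 | $19,500 | $487.50 | $243.75 | above $312.50, up to $556.25 |
| 10 | $39,000 | $975.00 | $487.50 | up to $312.50 |

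With V = $300 and 5 hours a week, the cost is 300 + 487.50 = $787.50 over 40 and 300 + 243.75 = $543.75 over 80. Both pass.

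With V = $300, the 40-patient figure stays within $800 while F ≤ 40 × (800 − 300) = $20,000. The 80-patient figure does so while F ≤ 80 × 500 = $40,000. The result differs only for F above $20,000 and up to $40,000.

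**Effect of adding the 5,967 count.** At 5 hours a week, 19,500/5,967 = $3.27, so the upper limit for V would rise from $556.25 to 800 − 3.27 = $796.73. The band would widen from 556.25 − 312.50 = $243.75 to 796.73 − 312.50 = $484.23. About half of the wider band thus comes from a count that the plan does not use for costing.

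**The case for a change.** The strongest opposing case is that the SAP itself makes this comparison a condition for proceeding, so the rule should be fixed in advance. Even between the two pilot counts it can reverse: with V = $300 and F = $30,000 (both assumed), the cost is 300 + 750 = $1,050 over 40 and 300 + 375 = $675 over 80. At 10 hours a week, IT support alone exceeds $800 over 40. One-time cost can matter too: with V = $300 and an assumed $60,000 over 80 patients, the figure is $1,050 if charged to one year and $550 if spread over three. The fuller economic analysis comes only after the decision.

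The arithmetic stands, and so does the observation that the divisor and the treatment of one-time cost are unwritten. It shows that a reversal can happen, not that the plan leads to a wrong one. The unit is a yearly cost of delivery, which points to recurring cost, and one-time IT cost is gathered as a separate item that can be reported separately. Nurse time is split by arm, so the costing is already built around the pilot patients. The 40-patient divisor is also the strictest: a cost that passes over 40 passes over every larger count.

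Showing IT cost over two divisors without saying which one decides would leave the rule as open as it is now.

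**Conclusion.** No change to the plan follows. The SAP leaves an allocation rule unwritten in a costing that it calls preliminary, and the rest of the text points an analyst to a sensible one: at most $800, recurring delivery cost, pilot patients as the divisor. On that reading the remaining uncertainty is a factor of 2 in one cost item. Whether that could change the result depends on IT hours, pay rates and other costs that the documents do not give. At the assumed $75 an hour, the affected range of other running cost is $605.00 to $702.50 at 2 hours a week and $312.50 to $556.25 at 5 hours.

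The primary outcome and the comparisons between arms are untouched. The SAP is written in the past tense and already gathers the cost items separately, so the cost report can state the count it divides by. The conclusion rests on the SAP text available for this review, part of which had been removed.
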